13.8 Adverse Event Reporting Requirements

The investigator or designee must report events to the Fred Hutch IRB in accordance with the policies of the IRB.

14.0 DATA AND SAFETY MONITORING PLAN

Institutional support of trial monitoring will be in accordance with the Fred Hutch/University of Washington Cancer Consortium Institutional Data and Safety Monitoring Plan (DSMP). Under the provisions of this plan, Fred Hutch Clinical Research Support (CRS) coordinates data and compliance monitoring conducted by consultants, contract research

organizations, or Fred Hutch employees unaffiliated with the conduct of the study. Independent monitoring visits occur at specified intervals determined by the assessed risk level of the study and the findings of previous visits per the institutional DSMP.

In addition, protocols are reviewed at least annually and as needed by the Consortium Data and Safety Monitoring Committee (DSMC), Fred Hutch Scientific Review Committee (SRC) and the Fred Hutch/University of Washington Cancer Consortium Institutional Review Board (IRB). The review committees evaluate accrual, adverse events, stopping rules, and adherence to the applicable data and safety monitoring plan for studies actively enrolling or treating subjects. The IRB reviews the study progress and safety information to assess continued acceptability of the risk-benefit ratio for human subjects. Approval of committees as applicable is necessary to continue the study.

The trial will comply with the standard guidelines set forth by these regulatory committees and other institutional, state, and federal guidelines.

15.0 DATA MANAGEMENT/CONFIDENTIALITY

The investigator will ensure that data collected conform to all established guidelines. Each subject is assigned a unique subject number to protect subject confidentiality. Subjects will not be referred to by this number, by name, or by any other individual identifier in any publication or external presentation. The licensed medical records department, affiliated with the institution where the subject receives medical care, maintains all original inpatient and outpatient chart documents.

16.0 STATISTICAL CONSIDERATIONS

16.1 Study Design

This is a randomized, controlled feasibility trial of acupuncture treatment delivered during planned chemotherapy infusion and 5-FU pump disconnect appointments, and self-administered acupressure plus oral cryotherapy compared to oral cryotherapy alone for prevention of CIPN.

16.2 Primary/Secondary Endpoints and Analytical Methods

16.2.1 Primary Endpoint

The primary endpoint is CIPN as measured by the EORTC-CIPN-20.

16.2.2 Secondary Endpoints

- Incidence of grade 2 or higher CIPN as measured by CTCAE version 5
- Severity of CIPN as measured by a Neuropen and tuning fork.
- Proportion of patients assigned to the intervention arm who complete 60% of acupuncture treatments.
- Incidence of pain, fatigue, nausea, and anxiety as measured by patient-reported (NCI PRO-CTCAE, BPI, oral dysesthesia) and provider-assessed (CTCAE version 5) grading scales.

16.3 Sample Size and Power

This is a pilot study in which preliminary estimates of CIPN severity will be obtained under two treatment conditions. Complete data from 50 patients will provide 80% power to detect a difference in EORTC-CIPN-20 of 0.7 standard deviation units, based on a t-test with 1-sided alpha=0.05. To account for 10% potential loss to follow-up, we will enroll 56 patients, 28 on the intervention arm of acupuncture/acupressure and 28 on the standard-of-care arm. Patients who enroll, but are not treated, or received less than one cycle of chemotherapy with associated study-specific treatment (including any planned acupuncture sessions for that cycle), may be replaced as detailed in section 11.0.

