| Population | 56 patients with a GI cancer malignancy with planned ≥3 months of a 5-FU- and oxaliplatin-based chemotherapy regimen. Eligibility criteria includes: 1) GI cancer (primary esophagus, gastric, pancreas, biliary, small bowel, appendix, colon, or rectal) scheduled to receive a new start of 5-FU, oxaliplatin, ± irinotecan [FOLFOX, FOLFIRINOX, FOLFOXIRI regimens] with plan for ≥3 months of therapy with the regimen, 2) age ≥18 years, 3) absolute neutrophil count >500 and platelet count >20,000, 4) not currently pregnant, 5) ability to understand and the willingness to sign a written informed consent document, 6) no baseline neuropathy from any cause, 7) no prior neurotoxic chemotherapy of any kind in the prior 3 years, 8) no planned initial dose of oxaliplatin <100% of the standard regimen-specified dose, 9) no receipt of acupuncture treatment in the prior 3 months, 10) no use of concomitant duloxetine for minimization of neuropathy, 11) no psychiatric illness/social situations that would limit compliance with study requirements. |
| Primary Endpoint | Chemotherapy-induced peripheral neuropathy as measured by the EORTC-CIPN 20. |
| Secondary Endpoints | 
 Incidence of grade 2 or higher CIPN as measured by CTCAE version 5. Severity of chemotherapy-induced peripheral neuropathy as measured by a Neuropen and tuning fork. Proportion of patients assigned to the intervention arm who complete 60% of acupuncture treatments. Incidence of pain, fatigue, nausea, oral dysesthesia, and anxiety as measured by the NCI PRO-CTCAE, Brief Pain Inventory (BPI), and CTCAE version 5. |

| | |
|-----------------------------|--|
| Type of control | Usual care + waitlist arm – receives no acupuncture during the 3-month intervention period |
| Investigation Drug | N/A |
| Dose | Acupuncture: 12 treatments with 30-minute needle retention |
| Route of administration | Acupuncture: filiform needle insertion |
| Regimen | 12 sessions of acupuncture. Acupressure training and self-treatment. |
| Trial Blinding | None |
| Treatment Groups | Arm A: Acupuncture + Acupressure Intervention with standard-of-care cryotherapy: acupuncture during chemotherapy infusion (day 1) and 5-FU pump disconnect (day 3) of each biweekly chemotherapy infusion x6 cycles (i.e. 12 acupuncture treatments over 12 weeks) + self-acupressure Arm B: Waitlist Control Arm with standard-of-care cryotherapy: 6 acupuncture sessions after the completion of the trial |

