9.1 Treatment Plan Overview

9.2 Acupuncture and Acupressure Intervention

The intervention group will receive acupuncture during chemotherapy infusion (day 1) and 5-FU pump disconnect (day 3) of each biweekly chemotherapy infusion x6 cycles (*i.e.* 12 acupuncture treatments over 12 weeks). Acupuncture treatments will be specifically targeted to prevent, treat, or mitigate neuropathy symptoms, pain, fatigue, nausea and anxiety. Patients will receive 30-minute acupuncture treatments in the seated or supine position. Standard acupoint techniques for point location²² will be utilized and Clean Needle Technique²³ will be followed using 32-40-gauge x 30-40mm Seirin acupuncture needles.

On day 1 the acupuncture points will be needled bilaterally at: ST36, SP6, LI10, GB40, P6, auricular shen men, and on the midline at Yin Tang (EX-HN3) and GV20. On day 3 the acupuncture points will be needled bilaterally at: LI4, LR3, ST36, SP6, LI10, GB40, P6, auricular shen men, and on the midline at Yin Tang (EX-HN3) and GV20. For patients unable to tolerate peripheral cryotherapy, the day 3 acupuncture protocol will be administered on day 1.

After the initial acupuncture treatment, the study acupuncturist will instruct the patient on how to locate and self-administer acupressure for key acupoints: bilateral LI4 (for pain, oral dysesthesia), bilateral P6 (nausea), and midline GV20 (fatigue). These acupoints are based on previously published studies,¹²⁻¹⁵ Traditional Chinese Medicine (TCM) theory,²² and current understanding of innervation and neuromodulation of acupoints.¹³ Auricular shen men points (anxiety) will be stimulated with vaccaria seeds applied by the acupuncturists on day 3 and removed after 4 days (day 7 of the cycle). Patients will be taught to self-administer an 11-minute acupressure regimen daily by stimulating each acupoint in a circular motion for 2 minutes on each bilateral points of LI4 and P6, 2 minutes on midline GV20, and to gently press the ear seeds on shen men for 30 seconds three times per day. The acupuncturists will provide additional teaching during the acupressure training on Cycle 1 Day 1 instructing the patients to utilize auricular Shen Men point during cryotherapy to help mitigate possible unpleasant effects of cryotherapy including: headache, toothache, and/or cold aversion/pain.

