If a patient misses an acupuncture session, it will not be made up. If a patient misses both sessions from 1 of chemotherapy, they will be removed from the study. Handouts describing acupuncture and acupressure will be provided to participants (Appendix L).

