11.0 SUBJECT DISCONTINUATION OF ACTIVE TREATMENT

Subjects may be removed from this study at any time at their discretion. Subjects may also be removed from this protocol if they develop any untoward side effects from the study procedures (acupuncture).

If a subject withdraws consent to participate in the study or aspects of the study, attempts should be made to obtain permission to record survival data up to the protocol-described end of the subject follow-up period. Documentation in the medical record should state that the subject is withdrawing from the study and what, if any, selected data the subject will permit the investigator to obtain.

If a subject withdraws consent and has received less than 1 cycle of chemotherapy with associated study-specified treatment (including any planned acupuncture sessions for that cycle), an additional patient will be recruited. Patients who receive less than 1 cycle of chemotherapy will not be followed.

An explanation for discontinuing treatment is recorded for each subject discontinuing treatment on the appropriate CRF/eCRF. The PI must be notified immediately if a subject discontinues treatment. All subjects, irrespective of treatment status, will continue to be followed for survival. Treatment in this study must be discontinued for any of the following reasons:

- at Investigator's discretion;
- at the subject's request;
- if the subject enrolls in a trial of another investigational agent which does not permit concurrent treatment;
- if the patient misses both acupuncture sessions from cycle 1 of chemotherapy;
- Grade 4 or life-threatening toxicity (See Section 13, Adverse Events) attributable to the study intervention;
- change in chemotherapy regimen which no longer includes oxaliplatin;
- pregnancy.

If a patient discontinues use of oxaliplatin, he/she may continue to receive acupuncture either weekly or as protocolized (twice weekly every other week) until the completion of 3 months duration of acupuncture treatment.

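### The replacement rule counts cycle 1 acupuncture sessions, which only Arm A has, and sections 16.3 and 11.0 disagree on the trigger; unless every randomised patient is kept, early non-adherers can be lost from Arm A alone

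*Combined protocol and SAP*

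**What the plan says.** Section 16.3 covers patients who are enrolled and never treated, and those who "received less than one cycle of chemotherapy with associated study-specific treatment (including any planned acupuncture sessions for that cycle), may be replaced". Its sentence ends by deferring to the other rule: "may be replaced as detailed in section 11.0".

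The rule in section 11.0 differs. It opens "If a subject withdraws consent and has received less than 1 cycle of chemotherapy with associated study-specified treatment" and concludes "including any planned acupuncture sessions for that cycle), an additional patient will be recruited". It therefore adds withdrawal of consent as a condition, and it is mandatory where 16.3 is permissive.

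Arm A has two sessions per cycle, "12 acupuncture treatments over 12 weeks" (section 9.2). The control arm "receives no acupuncture during the 3-month intervention period" (section 2.0). On missed sessions, section 9.2 says "If a patient misses an acupuncture session, it will not be made up". It then removes from the study a patient who misses both sessions of cycle 1. (A word is missing from that sentence; I read it as cycle 1 because section 11.0 does.) Section 11.0 lists the same event as a reason to discontinue treatment, which is not the same as leaving the study.

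On follow-up, section 11.0 says "Patients who receive less than 1 cycle of chemotherapy will not be followed", yet also says that all subjects, whatever their treatment status, are followed for survival.

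Sections 2.0, 6.3.2 and 16.2.2 define the adherence endpoint over patients assigned to the intervention arm; section 16.5 speaks more loosely of patients in that arm. No section defines an analysis population, says whether a replaced or removed patient stays in the CIPN-20 regression, or says whether an additional patient is newly randomised or fills the vacated place.

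**The concern.** Replacement and removal happen after randomisation, in an unblinded trial. Part of the trigger measures whether the patient took up the intervention, and it can be failed in one arm only. If patients who drop acupuncture early leave Arm A while comparable Arm B patients stay, the arms are no longer the groups that randomisation formed.

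Two results are exposed. The CIPN-20 comparison at 3 months could favour Arm A if those who leave would have had worse neuropathy. The feasibility result, a stated secondary objective, could lose the patients it most needs to count. The disagreement between 16.3 and 11.0 adds to this, because staff must choose which rule to apply when the allocation is already known.

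**Working it through.** **1. The plan's own figures.** Inputs from section 16.3: 50 patients with complete data (25 per arm), difference 0.7 SD, t-test, one-sided alpha 0.05, 10% loss. Noncentrality = 0.7 × √(25/2) = 2.47. Power is 78.7% from the exact noncentral t with 48 df, or 79.7% by the normal approximation, against the stated 80%. Enrolment = 50/0.90 = 55.6, so 56. The figures reproduce, and this point does not alter them.

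**2. The rules applied to patients who all had full cycle 1 chemotherapy.**

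| Patient | Replaced under 11.0? | Replaced under 16.3 alone? |
|---|---|---|
| Arm A, missed one cycle 1 session, stays | No | May be |
| Arm A, missed one cycle 1 session, withdraws consent | Yes, mandatory | May be |
| Arm A, missed both, does not withdraw consent | No, but removed under 9.2 | May be |
| Arm B, stays | No | No |
| Arm B, withdraws consent | No | No |

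If cryotherapy also counts as study treatment, it applies in both arms, and Arm A still carries the additional acupuncture condition. For patients with less than one cycle of chemotherapy itself, each rule reads the same in both arms.

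**3. Have these patients already failed the adherence endpoint?** 60% of 12 sessions is 7.2, so 8 sessions are needed. A patient who missed one session can still reach 11/12 = 92%; one who missed both in cycle 1 can still reach 10/12 = 83%. Neither has failed when the rule acts.

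**4. Adherence, assumed counts.** Suppose 22 of the final 28 Arm A patients reach 60%, and k others were replaced and all counted as non-adherent. The proportion over all assigned is 22/(28 + k), with exact 95% limits:

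- replaced patients left out: 22/28 = 78.6% (59.0 to 91.7)
- k = 2: 22/30 = 73.3% (54.1 to 87.7)
- k = 3: 22/31 = 71.0% (52.0 to 85.8)
- k = 4: 22/32 = 68.8% (50.0 to 83.9)

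The gap is 5 to 10 points. By step 3, this is the largest gap for each k, since some replaced patients might have reached 8 sessions.

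**5. CIPN-20, assumed counts.** If k of 28 + k Arm A patients are left out and would have scored d SD worse than the other 28, the Arm A mean is too favourable by d × k/(28 + k).

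- k = 1, d = 0.25: 0.25 × 1/29 = 0.009 SD; one-sided type I error 5.3%
- k = 4, d = 1.0: 1.0 × 4/32 = 0.125 SD; one-sided type I error 11.3%

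The error rates use the t-test with 25 per arm. For scale, the standard error of the difference is √(2/25) = 0.28 SD. The sign of d is assumed; if those who leave would have scored better, the bias runs against Arm A.

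**The case against.** The strongest reply is that 16.3 defers to 11.0, and 11.0 requires withdrawal of consent. A reader might infer that an Arm A patient who misses only the day 3 session and stays on study will be swapped out. The documents support that only if 16.3 is read without its closing reference. If 11.0 governs, the asymmetry is confined to patients who withdraw consent, and much of their 12-week data would be lost whether or not anyone else is recruited. That narrows the replacement point but does not close it: the texts still disagree, and the 9.2 removal rule needs no withdrawal.

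Second, recruiting another patient does not delete the first. No section says that a replaced patient leaves the analysis, and the adherence endpoint is worded over patients assigned to Arm A, which would keep them in the denominator. This stands for adherence, subject to the looser wording in 16.5. Nothing equivalent is said for the CIPN-20 comparison.

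Third, Arm B is not untouched by replacement: its untreated patients, and those with less than one cycle of chemotherapy, can be replaced as well. The sentence ending follow-up turns on chemotherapy alone, so it is the same in both arms and does not stop follow-up of an Arm A patient who had the chemotherapy but missed acupuncture. The conflicting sentence in 11.0 promises survival follow-up only, so it should not be read as a promise of symptom data.

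Fourth, section 9.9 gives patients who discontinue an end-of-treatment visit with the final questionnaires. For a patient removed after cycle 1, that visit falls before the next chemotherapy dose, so it does not supply a 3-month score.

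**Conclusion.** The point holds in a limited form. Both sections build Arm A's acupuncture sessions into the replacement trigger, they conflict on whether consent withdrawal is needed and on whether replacement is optional, and 9.2 adds a removal rule that only Arm A can trigger. With no stated analysis population, following these rules as written can lose early acupuncture non-adherers from Arm A only. If every randomised patient were followed and analysed as assigned, replacement by itself would not bias the comparison; the plan does not say that they will be.

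A reader might go further and infer that the trial selects for acupuncture adherers, or that reported adherence is overstated by 5 to 10 points. The documents do not support either as fact. The rules act on cycle 1 only, the endpoint wording already points to all assigned patients, and the number of early non-adherers is unknown. The illustrations (79% against 73% to 69%; 0.009 to 0.125 SD) rest on assumed counts, on every replaced patient being non-adherent, and on an assumed direction of effect.

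**What to change.** - State one replacement trigger, identical in 11.0 and 16.3, that reads the same in both arms and does not mention acupuncture sessions; for example, no oxaliplatin dose received after randomisation. Say once whether consent withdrawal is required and whether replacement is optional or mandatory.
- Randomise any additional patient 1:1 as a new subject, not into the vacated place.
- State in 16.5 that every randomised patient, including anyone replaced or removed under 9.2 or 11.0, stays in the assigned arm for the CIPN-20 comparison and, for Arm A, in the adherence denominator, in line with the endpoint wording in 16.2.2. Limiting this to patients for whom another is recruited would miss those removed under 9.2.
- Reconcile removal from the study in 9.2 with treatment discontinuation in 11.0, and the two follow-up sentences in 11.0, so that stopping acupuncture does not end collection of the 6- and 12-week CIPN-20 unless the patient refuses contact.

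The cost is protocol wording and some extra questionnaire contact. Fewer patients will qualify for replacement, the arms may end slightly unequal, and reported adherence may be lower.

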16.4 Randomization

Patients will be randomized 1:1 between the intervention arm and control arm.

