5.0 INTRODUCTION TO THE PROTOCOL

5.1 Introduction

Chemotherapy-induced peripheral neuropathy (CIPN) negatively impacts treatment delivery, both acutely (by requiring dose reductions, delays, or requiring early cessation of treatment) and chronically (by impacting quality of life for survivors). CIPN is a common side effect of oxaliplatin, which is a component of the majority of standard adjuvant and/or first-line metastatic therapies for gastroesophageal, pancreas, and colorectal cancer patients. In the MOSAIC trial of adjuvant 5-fluorouracil (5-FU) and oxaliplatin [FOLFOX], >90% of colon cancer patients reported CIPN during treatment, with 15% reporting symptoms four years later.¹ Similarly, in pancreas cancer patients receiving six months of 5-FU, irinotecan, and oxaliplatin [FOLFIRINOX] in the adjuvant setting, 61% had any-grade CIPN and 9-10% had grade 3+ CIPN in the landmark adjuvant and metastatic trials.^{2, 3} The high prevalence of acute and persistent CIPN in multiple gastrointestinal (GI) cancer patient populations highlights the need to more effectively mitigate acute and chronic CIPN.

In addition to peripheral neuropathy symptoms, as a result of oxaliplatin administration, patients can experience oral dysesthesia, which can negatively impact oral intake. Patients are typically educated to avoid cold foods and fluids, which can significantly impact food choices and eating/drinking overall during the acute symptoms of neurotoxicity.⁴ This is especially problematic in GI cancers, where digestion and oral intake are often compromised by the cancer itself.

Complementary therapies have been tested in the prevention and treatment of CIPN, with few effective treatments identified.⁵ Calcium and/or magnesium infusions with oxaliplatin were standard-of-care for prevention of CIPN, but were unsupported by a large randomized trial.⁶ Newer efforts have included both cryotherapy and acupuncture.

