6.4 Estimated Accrual

Fifty-six patients will be enrolled, 28 randomized to each arm.

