16.5 Statistical Analysis

Severity of CIPN (EORTC-CIPN-20 score) at 3 months will be summarized for each treatment arm, and treatment comparisons made via linear regression model with adjustment for baseline severity level. Adherence to acupuncture treatment among patients in the intervention arm will be described as a proportion with 95% confidence interval. Reasons for treatment non-adherence and delivered dose intensity of chemotherapy will be noted. Incidences of CIPN (grade 2 or higher), pain, fatigue,

nausea, and anxiety will be compared between treatment arms using Chi-squared or Fisher's exact tests as appropriate. As this is a pilot study, we will not have adequate power to adjust for covariates such as age, gender, and existing comorbidities.

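### Planned chemotherapy regimen is neither a randomization stratum in 16.4 nor a covariate in the 16.5 primary model, so a chance regimen imbalance stays in the CIPN-20 difference; one model term and stratified blocks would remove it cheaply.

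*Combined protocol and SAP*

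**What the plan says.** Section 16.4 is a single sentence: "Patients will be randomized 1:1 between the intervention arm and control arm". No section describes strata, block sizes, sequence generation or concealment. Equal arms are stated in three places (6.4, 9.0 and 16.3); 6.4 reads "Fifty-six patients will be enrolled, 28 randomized to each arm".

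Section 16.5 compares 3-month CIPN-20 between arms by linear regression with baseline severity as the only covariate. It declines further adjustment because "we will not have adequate power to adjust for covariates such as age, gender, and existing comorbidities". Regimen is not mentioned there, and delivered chemotherapy dose intensity is only to be noted.

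Section 7.1.1 admits FOLFOX, FOLFIRINOX and FOLFOXIRI and makes the planned regimen an eligibility item. Section 7.2.1 excludes baseline neuropathy. The background in 5.1 reports, for FOLFOX, that ">90% of colon cancer patients reported CIPN during treatment" and, for FOLFIRINOX in pancreas cancer, that "61% had any-grade CIPN and 9-10% had grade 3+ CIPN".

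**The concern.** The trial pools regimens whose cited neuropathy rates differ, and the regimen is on record for every patient before allocation. Neither the randomization nor the analysis uses it. The one covariate in the model cannot stand in for it: with baseline neuropathy excluded, baseline CIPN-20 should sit near its floor in nearly everyone.

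At about 25 analysed patients per arm, chance can leave the arms with noticeably different regimen mixes. If regimen affects CIPN-20, an arm with fewer patients on the more neurotoxic regimen looks better for that reason alone, and the planned analysis does not remove the difference. The error can run either way: part of an apparent benefit could come from regimen mix, or a real benefit could be partly hidden. Separately, the planned test gives up precision that a recorded variable could supply.

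**Working it through.** **The plan's own figure.** Section 16.3 states "Complete data from 50 patients will provide 80% power to detect a difference in EORTC-CIPN-20 of 0.7 standard deviation units". The planned test there is one-sided at the 5% level. With 25 per arm and SD 1, the standard error of the difference is √(2/25) = 0.283 and the noncentrality is 0.7/0.283 = 2.475. The noncentral t with 48 degrees of freedom gives power of 78.7%; the normal approximation gives 79.7%. Enrolment is 50/0.9 = 55.6, rounded up to 56, which agrees with "To account for 10% potential loss to follow-up, we will enroll 56 patients". The stated design is reproduced.

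**Inputs the documents do not give.** These are the regimen mix, the SD of CIPN-20 and the regimen gap on CIPN-20. I assume that the smaller regimen group is 20% to 50% of patients and that the gap is 0 to 1.0 SD. The upper end corresponds to reading 5.1 on a latent normal scale: probit(0.90) − probit(0.61) = 1.00. It is a bound for illustration, not an estimate.

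**How large a chance imbalance can be.** Fix the arms at 28/28 and let K of the 56 patients be in the smaller regimen group. The number falling in one arm is hypergeometric. With p = K/56, the between-arm difference in share has SD √(4p(1−p)/55).

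| Smaller regimen share (K) | SD of difference | P(difference ≥ 20 points, either direction) |
|---|---|---|
| 20% (11) | 10.7 points | 4% |
| 30% (17) | 12.4 points | 8% |
| 40% (22) | 13.2 points | 17% |
| 50% (28) | 13.5 points | 18% |

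The probabilities move in steps because only whole patients can move. At K = 11 and 17 the smallest qualifying difference is 7/28; at K = 22 and 28 it is 6/28.

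**What it does to the primary difference.** Shift = regimen gap × imbalance. For a 20-point imbalance:

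- gap 0: no shift
- gap 0.25 SD: 0.05 SD (7% of 0.7)
- gap 0.5 SD: 0.10 SD (14% of 0.7)
- gap 1.0 SD: 0.20 SD (29% of 0.7)

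The largest of these is 0.20/0.283 = 0.7 of the standard error of the difference.

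**Behaviour over all randomizations.** Simulation used 20,000 runs per setting, 25 per arm, 40% on the irinotecan-containing regimen, total SD 1 and gaps of 0, 0.5 and 1.0 SD. Without strata and without a regimen term, type I error was 4.7% to 5.1% and the mean estimate was about 0.70 for a true 0.70. The procedure is valid on average.

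**What the fix gains.** A regimen term reduces the residual SD to √(1 − g² × 0.4 × 0.6) for a gap of g: 1.000, 0.969 and 0.872 at g = 0, 0.5 and 1.0. With exact balance within strata, the noncentralities are 0.7/(0.283 × residual SD) = 2.475, 2.553 and 2.839, on 47 degrees of freedom. For the term without strata, power is averaged over the hypergeometric imbalance.

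| Regimen gap | As planned | Regimen term only | Strata and term |
|---|---|---|---|
| 0 | 78.7% | 77.9% | 78.6% |
| 0.5 SD | about 79% | 80.1% | 80.8% |
| 1.0 SD | about 79% | 86.9% | about 88% |

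The simulation agrees to within about half a point. Stratifying without the term at a 1.0 SD gap gave type I error of 2.8% and power of 81%: the test becomes conservative, and most of the gain is lost.

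**The case against.** The strongest reply is that the documents do not show that regimen predicts the primary endpoint. The two rates in 5.1 come from separate trials in different cancers, so regimen is confounded with disease and with the way neuropathy was reported. They are any-grade incidences, the 61% over six months of treatment, not CIPN-20 severity at 3 months. Section 7.2.3 gives one starting oxaliplatin dose for most regimens, and FOLFOXIRI has no cited rate. All of this stands. A reader might take 5.1 to establish a 1.0 SD regimen effect; it does not, and zero is not excluded.

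A reader might also infer from 16.4 that allocation is unrestricted, so that 28/28 would be unlikely. Under coin-flip allocation of 56 patients, exactly 28/28 would occur 10.6% of the time. But 16.4 does not say this, and three statements of 28 per arm point to some restriction. Only the absence of a described method can be held against the plan.

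A third tempting reading is that the trial is biased or its false-positive rate inflated. Error rates do rise if one looks only at unlucky allocations, but that is true of any prognostic variable, and the test allows for it across all allocations.

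Finally, this is a pilot that declines covariate adjustment on power grounds, and regimen can still be tabulated by arm. Tabulation would reveal an imbalance but not correct the estimate. The power argument does not carry over to a single regimen term, which costs under 1 point even when regimen has no effect.

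**Conclusion.** The point holds as a cheap improvement, not as a flaw that invalidates the design. Planned regimen is available before allocation and is used in neither the randomization nor the primary model, so a chance imbalance is left in the CIPN-20 difference. With 28 per arm, an imbalance of 20 points or more has a probability of about 4% to 18% for a smaller-group share of 20% to 50%. An imbalance of exactly 20 points moves the arm difference by 0 to 0.2 SD for an assumed regimen gap of 0 to 1.0 SD; a larger imbalance moves it proportionately more.

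The consequence is conditional and a matter of precision. The estimate is unbiased over randomizations and overall type I error stays near 5%. The size depends entirely on a regimen mix and gap that the documents do not supply. The power figures also take a 40% irinotecan-containing share, 25 evaluable patients per arm and no contribution from baseline CIPN-20. Most of the recoverable gain lies in 16.5 and less in 16.4.

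**What to change.** In 16.5, add planned regimen (FOLFOX versus irinotecan-containing) to the primary linear regression beside baseline CIPN-20. State that this is the planned regimen recorded before randomization, so that later treatment changes do not alter the covariate.

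In 16.4, replace the sentence with wording such as: Patients will be randomized 1:1 in permuted blocks of randomly varying size (4 or 6), stratified by planned regimen (FOLFOX versus irinotecan-containing); the list and block sizes will be concealed from enrolling staff. This also supplies the missing description of the method.

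The cost is two concealed lists instead of one and one extra model term, with no added patients or visits. If regimen has no effect, the power loss is about 1 point or less. Incomplete final blocks may leave the arms slightly unequal. If enrolment has already begun, the model term alone, specified before the outcome data are examined, keeps most of the benefit. Strata should not be introduced without the matching term.
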